4. INNOVATION

The means by which the current proposal addresses a widely prevalent problem (i.e., Pain comorbid with PTSD), and a national crisis (i.e., opioid addiction following pain treatment), is highly innovative, both in terms its treatment integration, and in terms of its use of select biomarkers to specify mechanisms of improvement.

5. METHODS (describe the primary plan for data collection, measurement tools, and timelines)

Design Overview and Project Timeline: The study team will first integrate home-based tDCS into two of the early weeks of the 12 week sessions of PE protocol. The reasoning to conduct tDCS in this way related to PE are three folded: first, controlling signaling of pain to engage into trauma treatment may reduce dropout from PE; second, research shows some cognition improvement with tDCS which may help patients to understand and more adequately participate in aspects PE treatment particularly as the complete understanding of the rationale of PE at the beginning of the treatment is very important to set the stage for treatment expectation and prevent dropout, and finally the hypothesized model of interaction of chronic pain and PTSD symptomatology, tDCS may help to reduce avoidance behavior modulated by pain and PTSD symptoms. This will be followed by a repeated measures single group design wherein each of the 15 Veteran participants serves as their own control, with major assessments of feasibility, clinical and biomarker indices at pre, mid and post-treatment (week 13), complemented by weekly assessments of key pain and PTSD symptoms. The study will also include with open ended key informant interviews following treatment with the 15 participants to derive suggestions for improving the integrated treatment

5.2 Participants & Inclusion / Exclusion Criteria: Participants will be Veterans, age 18 years and older, presenting with PTSD and Pain. **Inclusion Criteria** are: 1) Presence of chronic non-cancer pain and pain interference, defined as scoring 1 standard deviation above PROMIS⁵⁵ normative data on both the 3-item PROMIS Pain Intensity 3a scale⁵⁵ and the 8-item PROMIS Pain 8a Interference scale⁵⁵ (see Measures below). Symptoms will be required to be of six-month duration or longer; 2) Diagnosis of PTSD assigned on the basis of the Clinician Administered PTSD Scale⁵⁶. **Exclusion Criteria** are: 1) Having a household member who is already enrolled in the study; 2) Active psychosis or dementia at screening; 3) Suicidal ideation with clear intent; 4) Current substance dependence; 5) current opioid medication for pain 6) being pregnant.

5.3. Recruitment and Retention Procedures: will be addressed in the larger proposal derived from pilot.

5.4. Minority and Female Recruitment: At least 25% of the sample will be non-white and 10% female.

5.5. Description of the Informed Consent Process: Informed consent will be administered in private UTH TRC offices by approved individual trained in human subjects regulations and informed consent procedures. If any participants are illiterate, the consent will be read and explained in the presence of a witness. Teleconsent will also be used when the potential participant is unable to come to the office for the first visit of enrollment and to address unforeseeable circumstances, such as the current covid19 crisis. The potential participant will digitize (scan or photograph) a version of the consent they sign, or use a digital signature such as that found in Adobe to sign the consent document. This digitized document and signature will then be sent via email, or the hard copy will be sent via US postal service mail to the person consenting the potential participant.

5.6. Attrition and Retention efforts: Will be addressed in the larger proposal derived from this pilot.

5.7. Medication Stabilization. Patients will be asked to maintain medications at current dosages for at least 4 weeks prior to starting the trial.

5.8. Participant Payment: All participants will receive \$30 for baseline and \$30 for midpoint, \$30 for the post-treatment clinical and biomarker assessments (insufficient time for follow-up), \$15 for tDCS turn over and assessment, and \$25 for the feasibility interview. Transportation/parking in the amount of \$12 will be designated for the four in person visits.

5.9. Treatment: tDCS and PE Integration:

Overview of tDCS: tDCS is a non-invasive neuromodulation technique that has been used to improved cognitive functions. will be administered with a constant current intensity of 2 mA⁵⁷ for 20 min per session/ 10 sessions total daily for 2 weeks (Monday to Friday), the device is a Soterix 1x1 tDCS mini-CT Stimulator (Soterix Medical Inc., NY) with headgear and 5 _ 7 cm saline-soaked surface sponge electrodes. The sponge electrodes snap into the custom headgear, which is secured to the participant's head for simple and fail-safe electrode preparation. This single-position headgear with clearly labeled sponge markers eliminated room for user error and helped conserve the placement of the montage. Participants will administer a stimulation session via the Soterix 1x1 tDCS mini-CT Stimulator only after being provided a single-use code to unlock the device by the research staff once proper contact quality is achieved (only the on/off button will be adjustable by the study participants; they will not be able to adjust the device settings). After the participant enters the unlock code, the screen on the device will show a timer that counted down the minutes until the end of the session. After 20 min, the device will turn off automatically, and the study staff will instruct the participant to remove the headset and discard the sponges and to safely store all materials for the next session.

Overview of PE: Prolonged Exposure has been extensively researched, including by the present team (see Acierno et al.⁵⁸), and is an effective treatment for PTSD⁵⁹ that includes the following components: a) psycho-education about the common reactions to traumatic events and presentation of the treatment rationale (sessions 1 and 2), b) repeated *in vivo* exposure to traumatic stimuli (*in vivo* exercises are assigned as homework during sessions 3 through 11), c) repeated, prolonged, imaginal exposure to traumatic memories (imaginal exposure is implemented during sessions 3 through 11; patients listen to session audiotapes for homework between sessions), and d) relapse prevention strategies and further treatment planning (session 12). The manual for PE is publicly available.

Integration of tDCS and PE: Participants will come in person to the clinic office to complete the baseline visit and the in-person training for the use of both home-based self-administered tDCS and the home-based telehealth device (iPad) for the PE sessions. They understand that they will start the sessions of tDCS once they start the *in vivo* and imaginal exposures assignments at home. They will self-administer (under televideo supervision) the

tDCS session before doing in vivo and/or imaginal exposures assignments. The participants will be remotely supervised by trained research staff at each stimulation to ensure the technique is correct and to monitor any adverse events. We will provide secure videoconferencing software (e.g., WebEx) and ensure the participants are comfortable using the telehealth software.

5.10 Dependent Measures / Feasibility, Biomarker, and Clinical (note description has been eliminated)

1. Demographics (pre-treatment only): age, race, ethnicity, sex, marital status, education, disability status, income, and employment information will be collected via a study specific demographic form.
2. Recruitment Metrics: defined as the rate of participant enrollment per week.
3. Biomarker Sample Collection: defined as the % of samples collected at major assessment points.
4. Feasibility of establishing biomarker relationship to hypothesized mechanisms of change: defined as ability to collect viable samples for analysis.
5. Treatment Attrition: defined as the % of participants dropping out prior to completing 12 sessions of the intervention protocol. We will also collect number of sessions completed.
6. Rate of Missing Data: defined as % of missing data (# missing items aggregated across all self-report measures divided by total number of possible items) at each measurement time point.
7. Treatment Satisfaction: as measured by the Charleston Psychiatric Outpatient Satisfaction Scale: CPOSS⁶⁰.
8. Treatment Credibility: defined as an overall scale rating from 0 to 10 with 0 being '*not credible, I did not think this treatment would help either my PTSD or Pain symptoms*' to 10 being "*completely credible, I was very sure this treatment would help both my PTSD and Pain symptoms*".
9. Treatment Acceptability: defined as an overall scale rating from 0 to 10 with 0 being '*not acceptable, this treatment should not be offered to veterans, those in pain, or those with PTSD*' to '*completely acceptable*' "*this treatment is perfectly suited to veterans and others with Pain and PTSD symptoms*."
10. General Pain Information (Major Assessments): general information about chronic pain will be gathered to include location of pain site(s), duration of chronic pain at each site, current and prior treatment approaches for chronic pain, medical visits related to pain management, and past pain medications.
11. PROMIS Pain 3a Intensity Scale⁵⁵ (Weekly during Treatment + Major Assessments)
12. PROMIS PAIN 8a Interference Scale⁵⁵ (Weekly during Treatment + Major Assessments)
13. The Clinician-Administered PTSD Scale 5 (CAPS-5)⁶¹ (Major Assessments)
14. PTSD Checklist-5 (PCL-5)⁶¹ (Major Assessments)
15. PHQ-9⁶² (Weekly during Treatment + Major Assessments)
16. World Health Organization Quality of Life – Short Form (WHOQOL-BREF)⁶³ (Major Assessments)

To permit comparison with prior pain research, but to limit participant burden, the following additional pain related scales will also be used only at major assessment points:

17. The West Haven-Yale Multidimensional Pain Inventory: (Major Assessments) (WHYMPI/MPI)⁶⁴
18. The Tampa Scale of Kinesiophobia-Revised (TSK-R)⁶⁵ (Major Assessments)
19. Pain Catastrophizing Scale (PCS)⁶⁶ (Major Assessments)
20. Homework Diary (Weekly During Treatment): Daily records of tDCS and PE homework completion will be maintained so as to permit 'dose as delivered' effects of treatment.
21. Biomarker Assessments (Baseline, Mid-Point, Post-Treatment and Follow-ups): Salivary levels of the biomarker panel (cortisol, substance P, DHEA, IL-1, and IL-6) using enzyme-linked immunosorbent assays (ELISA).

Saliva Sample Collection (All major assessments): Saliva samples will be collected through a passive drool method at the beginning and end of Baseline (first week), Mid-Point (week 6), and Post (week 12)-Treatment. Saliva will be naturally allowed to accumulate in the oral cavity and the participant will discharge it into the specimen tube (2 mL capacity) with lid.

Immediately after collection the collected saliva samples will be placed on ice and store at -80 degree C until analysis.

Salivary Biomarker Measurement (All major assessments): Owing to their possible involvement in pain and/or PTSD (see Background section), the following biomarker panel will be assessed in saliva: cortisol, substance P, DHEA, IL-1, and IL-6.

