Primary Feasibility Analyses *Feasibility Hypothesis SA1) 75% of Veterans experiencing Pain and PTSD who enroll in the Pilot will complete the integrated treatment (at least 8 sessions) and both completers and dropouts will offer actionable suggestions in focus groups for improving the delivery of the intervention.* We will report the % of veterans who complete the integrated tDCS+PE protocol. We will report the rate of treatment completion, including a description of number of sessions completed prior to dropping out at the patient level (with 12 sessions completed being 100% treatment complete/not dropout). In addition to overall measures of treatment completion (i.e., session attendance), we will also collect measures of treatment adherence, as measured by percent of returned, completed homework record forms for tCBS and exposure practices in terms of actual daily assignments completed. All these measures will also be reported in terms of Race and Sex. *Feasibility Hypothesis SA1) Feasibility metrics will be acceptable for recruitment rate (2 per month), treatment completion (75%), assessment completion (90%), and good to excellent satisfaction (95%).* A key feature of the proposed feasibility study is demonstration that recruitment of eligible participants is possible for a future large scale RCT. Thus, we will report all aspects of CONSORT data in addition to the number of referrals obtained each week. Finally, we will report the overall % of missing data at the item level, and the rate of assessment completion and partial completion at each time point to examine if assessment timing is optimal. SA1 also includes effective collection and use of stress biomarker samples. Finally, Descriptive data on rates / scores for satisfaction, credibility, and acceptability will be reported.

6. SUMMARY and SPECIFIC AIMS for ENSUING GRANT APPLICATION (Page 6)

SPECIFIC AIMS

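### Section 5.13 scores tDCS adherence from returned homework forms although staff unlock and supervise every stimulation, so reported delivery can differ from stimulation given

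*Combined protocol and SAP*

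**What the plan says.** Three parts of the combined protocol and SAP bear on this.

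- **Section 5.10, item 20 (Homework Diary).** "Daily records of tDCS and PE homework completion will be maintained so as to permit 'dose as delivered' effects of treatment". The item covers tDCS and exposure homework together and does not say whether participants or staff keep the records.
- **Section 5.13, Primary Feasibility Analyses.** Treatment adherence is the "percent of returned, completed homework record forms for tCBS and exposure practices in terms of actual daily assignments completed". The abbreviation tCBS is read here as tDCS. The text does not say how an unreturned form is counted.
- **Section 5.9, Overview of tDCS and Integration of tDCS and PE.** The schedule is "20 min per session/ 10 sessions total daily for 2 weeks (Monday to Friday"). A participant can start a session "only after being provided a single-use code to unlock the device by the research staff once proper contact quality is achieved". "The participants will be remotely supervised by trained research staff at each stimulation". At the end, "After 20 min, the device will turn off automatically, and the study staff will instruct the participant to remove the headset".

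The other completion measures are the milestone of at least 8 sessions, attrition before 12 sessions, and session attendance. All refer to the 12-session treatment protocol, not to the 10 stimulations.

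**The concern.** A diary is a reasonable source for exposure homework, which nobody on the study team watches. For tDCS it is the weaker of two available sources. Staff release each stimulation, supervise it and are in contact when it ends, so they can record every start and finish at first hand. The adherence measure in section 5.13 nevertheless runs through a form that has to come back.

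Whether supervised tDCS can be delivered at home alongside PE is a central feasibility question of this pilot. A participant could reach 8 treatment sessions with any number of stimulations, so the completion milestone does not answer it. The diary and its forms are the only stated source on tDCS delivery. If forms go missing, that figure mixes paperwork with delivery, and a later trial would be planned on the mixture.

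**Working it through.** **Inputs from the documents.** 15 participants in a single group; stimulation Monday to Friday for 2 weeks; 20 minutes each (sections 5 and 5.9).

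**Planned dose.** 5 × 2 = 10 stimulations per participant, which reproduces the plan's figure. That is 10 × 20 = 200 minutes per participant and 15 × 10 = 150 stimulations in all.

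**Assumptions.** The documents give no form-return rate, so every rate below is assumed. Each scheduled stimulation is taken to have one form entry, and returned entries are taken to be accurate.

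**Two readings of the section 5.13 measure.**
- Reading A: returned and completed entries ÷ scheduled stimulations. Unreturned entries count as not done.
- Reading B: completed entries ÷ returned entries. Unreturned entries leave the denominator.

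**Reading A, forms missing at random.** Reported mean = stimulations delivered × return rate.

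| Delivered (mean of 10) | Assumed return rate | Reported mean | Reported total of 150 |
|---|---|---|---|
| 10 | 90% | 9.0 | 135 |
| 10 | 80% | 8.0 | 120 |
| 10 | 70% | 7.0 | 105 |
| 10 | 50% | 5.0 | 75 |
| 8 | 80% | 6.4 | 96 |

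**Reading B, missed stimulations falling on unreturned forms.** A participant given 7 of 10 who returns 7 completed entries is reported as 7/7 = 100%.

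**Worked example with dropouts.** Twelve completers have 10 stimulations each and return all forms. Three dropouts have 5 each.
- Truth: 12 × 10 + 3 × 5 = 135; 135/150 = 90%.
- Dropouts return nothing: Reading A gives 120/150 = 80%; Reading B gives 120/120 = 100%.
- Dropouts return entries for the 5 they had: Reading A gives 135/150 = 90%, which is correct; Reading B gives 135/135 = 100%.

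The error can go either way. Under Reading A it is zero when all forms for delivered stimulations come back and are accurate. Under Reading B, forms for missed stimulations must come back as well.

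**Staff count.** Counting supervised stimulations gives 135/150 = 90% in every version of the example, whatever the form return.

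**The case against.** The strongest reply is that two statements are being joined. Returned forms appear only in section 5.13, as the measure of adherence. Item 20 does not say who maintains the diary, and staff-kept or staff-checked records would fit its wording. A reader might infer that the plan scores dose as delivered from participant-returned forms. The documents do not say that; they only name no other source for it. This part of the reply stands.

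The adherence wording also refers to assignments actually completed, so it is not a bare return rate. That is fair, but the count of completed assignments still comes from the returned forms.

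A staff log may exist in practice. Part of the Methods section was not available for this review, and the heading of 5.10 says that measure descriptions were left out. A reader should not conclude that no log is kept, nor that the form is a tick-box that cannot show an early stop, because its layout is not shown. But section 5.13 names the form as the measure, so an unmentioned log would not alter the reported figure.

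Zero return from all dropouts is the unfavourable end of the range. The diary is scheduled weekly, so someone leaving after 5 stimulations could already have handed in a week. The documents do not show that dropouts return fewer forms; that is an assumption of the example.

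Finally, the consequences are limited. The stated milestones concern completion of at least 8 sessions (75%), actionable suggestions at exit, recruitment, assessment completion (90%) and satisfaction (95%). Section 5.13 specifies no dose-response analysis. A reader might infer that the completion milestone, or a planned dose analysis, is biased. Neither follows.

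**Conclusion.** The point holds for the adherence measure in section 5.13. As written, reported tDCS delivery depends on form return, although each stimulation passes through staff who could count it. For dose as delivered it holds less firmly: item 20 names the diary and no available text names an alternative, but who keeps the diary is left open.

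The size cannot be fixed from the documents because no return rate is given. Under the assumed example the reported figure is 80% or 100% against a true 90%. With complete and accurate forms it would be correct. The documents do not show that the reported dose will be wrong, only that it can be, in a direction set by an undefined denominator.

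The measure is descriptive and no milestone changes. The change is still worth making, because delivery figures are a main product of a feasibility pilot and the better source is already at hand.

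**What to change.** In item 20 of section 5.10 and in section 5.13:

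1. Take tDCS delivery from a staff record of each supervised session: code issued (yes/no) and minutes delivered out of 20.
2. Report stimulations started and stimulations completed, each out of 10, per participant for all 15 enrolled, dropouts included. State that denominator.
3. Use this count in any dose-as-delivered summary.
4. Keep the diary for exposure homework and for showing whether tDCS and exposure fell on the same day. A joint daily diary holds that timing, so tDCS should not be dropped from it.
5. Report form return as a separate metric, and say who keeps the diary.

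The cost is a few lines of text and one log line per stimulation, at most 150 lines, written by staff who are already supervising. No visit or participant task is added. The change concerns measurement only and leaves the stimulation schedule and clinical management as they are.

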5.11. Post treatment Key informant interview procedures and Integration of Feedback

A standardized series of queries will be used to prompt participants to comment on various aspects of the intervention integration and how it might be approved. Additional information will be provided in the larger proposal derived from this pilot.

5.12. Treatment Providers / Interviewers / Consent Procedures: Project therapist will have a master's degree or higher in clinical psychology, counseling, or social work and be certified to deliver PE. All treatment sessions will be audio-taped and 15% of these will be randomly selected and rated for adherence. The PI or Research Assistant will conduct the consent procedures and initial eligibility (i.e., baseline) diagnostic assessments for the study. The Research Assistant will conduct all major assessments. All assessments will be audio-taped and study personnel will listen to a randomly selected 20% to ensure reliability of CAPS diagnosis over the course of the study. Pilot trials of this assessment battery indicate that major assessments will take between 75 and 90 minutes.

5.13. DATA ANALYSIS PLAN (provide a detailed description of how the data will be analyzed, focusing specifically on how the data analytic approach is suited to answer the study aims)

Analysis Sets & Treatment of Missing Data: Participants who terminate early will be asked to complete follow-up interviews and their data will be included in analyses following intent to treat standards.

Descriptive Analyses Putative prognostic variables that will be investigated through these descriptive analyses include: demographic factors, number/type of comorbid diagnoses, participation in non-study treatment for comorbid psychopathology, medications (by class), and initial (baseline) intensity/severity levels for the primary outcome variables: pain severity, pain interference, and intensity of PTSD (PCL), avoidance behaviors, and whether non-study treatments were received for psychopathology symptoms. To investigate potential limits on generalizability, we will compare demographic characteristics of those who decline to participate with those who participate.

Primary Feasibility Analyses *Feasibility Hypothesis SA1) 75% of Veterans experiencing Pain and PTSD who enroll in the Pilot will complete the integrated treatment (at least 8 sessions) and both completers and dropouts will offer actionable suggestions in focus groups for improving the delivery of the intervention.* We will report the % of veterans who complete the integrated tDCS+PE protocol. We will report the rate of treatment completion, including a description of number of sessions completed prior to dropping out at the patient level (with 12 sessions completed being 100% treatment complete/not dropout). In addition to overall measures of treatment completion (i.e., session attendance), we will also collect measures of treatment adherence, as measured by percent of returned, completed homework record forms for tCBS and exposure practices in terms of actual daily assignments completed. All these measures will also be reported in terms of Race and Sex. *Feasibility Hypothesis SA1) Feasibility metrics will be acceptable for recruitment rate (2 per month), treatment completion (75%), assessment completion (90%), and good to excellent satisfaction (95%).* A key feature of the proposed feasibility study is demonstration that recruitment of eligible participants is possible for a future large scale RCT. Thus, we will report all aspects of CONSORT data in addition to the number of referrals obtained each week. Finally, we will report the overall % of missing data at the item level, and the rate of assessment completion and partial completion at each time point to examine if assessment timing is optimal. SA1 also includes effective collection and use of stress biomarker samples. Finally, Descriptive data on rates / scores for satisfaction, credibility, and acceptability will be reported.

6. SUMMARY and SPECIFIC AIMS for ENSUING GRANT APPLICATION (Page 6)

SPECIFIC AIMS

Overview: Chronic pain is among the most pervasive and expensive health complaints in the United States^{67,68}. Veterans, especially those who present with Post-Traumatic Stress Disorder (PTSD), are particularly likely to experience chronic pain^{69,70}. Moreover, pain in the form of fibromyalgia diagnosis is actually a component of Gulf War Syndrome, and is highly comorbid with other common military service-related health problems such as Posttraumatic Stress Disorder (PTSD)⁶. While effective non-pharmacological treatments for each disorder exist independently^{71,72}, there are no integrated treatments for Pain and PTSD; this despite recognition of the primacy of pain complaints in combat Veteran populations⁶⁹. Moreover, evidence-based non-pharmacological treatments for pain, per se, are effective in only about 50% of cases, with recent meta-analysis findings indicating no significant maintenance of effects at 6 or 12-month followup⁷³. Therefore, we propose to (a) refine & (b) gather feasibility data for an integrated mind-body intervention for Pain and PTSD: **tCBS+Prolonged Exposure**, with the prediction that integrating these treatments will enhance overall efficacy.

Given its frequent co-occurrence with mental health conditions, pain is often conceptualized within a biopsychosocial model to explain the multiple dynamic and complex influences that impact its presentation and exacerbation⁷³. Extending this model to PTSD supports the conceptualization of a mutual maintenance loop between pain and PTSD, and suggests the potential benefit, or perhaps, necessity of an integrated treatment for

both disorders, as common mechanisms may underlie symptom exacerbations for both Pain and PTSD⁷⁴. Indeed, integrating innovative, non-pharmacological, non-invasive interventions such as tDCS with an evidence-based treatment for PTSD may produce short-term and long-term benefits in both PTSD and pain symptoms by addressing shared mechanisms.

Thus, the Overall Aim of the present proposal is to integrate, refine and investigate the feasibility (e.g., pilot testing, recruitment, randomization, attrition, assessment, etc.) of combining a non-pharmacological, non-invasive and short technique for treating pain (tDCS) and a best practices evidence-based treatment for PTSD (i.e., Prolonged Exposure: PE) in Veterans. Establishing feasibility will justify future work directed toward assessing the ability of the combined treatment to ameliorate the impact of shared hyperarousal and avoidance symptoms (e.g., pain mediated avoidance and anxiety/fear mediated avoidance; hyperarousal driven pain intensification). Moreover, standard psychological PROMIS measures of pain and PTSD will be complemented by stress-related salivary biomarkers before, during, and after treatment to test feasibility and relevance of these measures on pain ratings and PTSD symptoms. Whereas PE and the tDCS techniques already exist, the integration of these strategies into a treatment of acceptable duration, interaction and character must first be achieved and pilot tested as proposed here.

Toward this end, the Specific Aims of the present proposal are to:

SA1a: *Integrate and Pilot the tDCS+PE treatment.* The investigative team is comprised of Pain, PTSD, and salivary biomarker experts who will integrate tDCS and PE into a 12 session tDCS+PE treatment which will undergo subsequent pilot testing with 15 Veterans with significant ratings of pain and PTSD diagnosis. Post treatment key informant interviews will be conducted where suggestions for treatment enhancement and satisfaction will be systematically collected and integrated into the intervention.

SA1b: *Test the feasibility of both the intervention and key study design features.* The investigators will evaluate the feasibility of the integrated tDCS+PE intervention in treating Pain and PTSD measured in terms of recruitment metrics, randomization processes, assessment burden, salivary biomarker collection, specification of biomarker relationship to hypothesized mechanisms of change, treatment attrition, rates of missing data at each measurement time point, participant satisfaction, and ratings of treatment face validity..

SA2: *Observe a preliminary signal of treatment effects in terms of Pain and PTSD symptoms.* We will derive preliminary effect size approximations associated with intervention and comparison conditions in terms of primary symptom outcome measures.

Specific hypotheses include: **SA1a)** 75% of Veterans experiencing pain and PTSD who enroll in the Pilot phase will complete the integrated treatment and both completers and dropouts will offer actionable suggestions in focus groups for improving the delivery of the intervention. **SA1b)** Feasibility metrics will be acceptable for recruitment rate (4 per month), successful randomization (100%), treatment completion (75%), assessment completion (90%), and good to excellent satisfaction (95%). **SA2)** A preliminary signal based on baseline to post-treatment symptom changes for pain and PTSD measures will be acquired.

REFERENCES

3. Gauntlett-Gilbert, J., & Wilson, S. (2013). Veterans and Chronic Pain. *British Journal of Pain*, 7(2), 79-84. doi: 10.1177/2049463713482082
5. Nahin, R. (2017). Severe Pain in Veterans: The Effect of Age and Sex, and Comparison with the general Population. *The Journal of Pain*, 18(3), 247-254. doi: 10.1016/j.jpain.2016.10.021

6. Kuzma, J.M., & Black, D.W. (2006). Chronic Widespread Pain and Psychiatric Disorders in veterans of the First Gulf War. *Current Pain and Headache Reports*, 10, 85-89.
